**Study Exemption from IND Requirements per 21 CFR 312.2(b) is pending**

## ABSTRACT

Lymphatic malformations (LMs) arise from abnormal development of lymphatic vasculature. Associated morbidity can be severe, including bleeding, sepsis, airway and visual axis obstruction (cervicofacial LMs), respiratory compromise (thoracic LMs), ascites and malabsorption (peritoneal/pelvic LMs), and limitations on mobility (extremity LMs). Severe symptoms can be life-threatening. Treatment options are often palliative and recurrence is common [1, 2]. Recently, results in our laboratory demonstrated that propranolol, a pan beta-adrenergic receptor ( $\beta$ BAR) antagonist, had cytotoxic and anti-proliferative effects against cells isolated from LM tissues. Preliminary results from treating symptomatic LM patients at our institution with propranolol at a dose range from 0.7-1mg/kg/day demonstrated a 70% positive response rate, with patients reporting improvement in their symptoms.

Despite severe morbidities and even mortality, there are no effective, objective, repeatable diagnostic tools to evaluate lymphedema severity, and there is no FDA-approved medical treatment for this devastating condition. Thus, we hypothesize that quantitative magnetic resonance (QMR) can accurately and quickly evaluate lymphedema severity, and propranolol will be effective in improving lymphedema, using QMR as a treatment response evaluator.

QMR has been validated in obesity research but has never been validated for lymphedema. It has the ability to quantify total body water, extracellular and intracellular water. Lymphedema results when there is excess, pathological accumulation of fluid in the interstitial spaces (extracellular water). Therefore, QMR has the potential to sensitively and accurately quantify the severity of extracellular water accumulation, thus severity of lymphedema.

Propranolol has been used for different indications for many years. Most recently, propranolol gained FDA approval for use in infants with hemangiomas, a related vascular anomaly (Hemangeol ®) (<http://www.accessdata.fda.gov/scripts/cder/drugsatfda/index.cfm?fuseaction=Search.DrugDetails>, accessed May 23, 2014). FDA-approved dose range for treating hemangiomas in infants (>5 weeks old, >2kg) ranged from 1-3mg/kg/day in divided doses. Propranolol has also been used to treat pediatric supraventricular tachycardia at doses up to 4mg/kg/day[3, 4]. However,  $\beta$ AR antagonists are not without potential adverse effects, including hypotension, bradycardia, hypoglycemia, bronchospasms, and sleep disturbances[5].

The dose range of 0.7-1mg/kg/day was chosen for our LM patients as it was the low end of dose range for infants treated with propranolol for problematic hemangiomas. At this dose, no significant hemodynamic adverse effects were noted in our LM patients. However, when patients stopped propranolol or their dose fell below 0.7mg/kg/day, they suffered rebound worsening of their symptoms. Moreover, inflammatory events such as infections temporarily overcame the effects of 0.7-1mg/kg/day of propranolol. Thus, it is unknown whether we have achieved maximum propranolol efficacy at our current dose range. We propose to escalate propranolol dosages up to 3mg/kg/day in this study, still well below the dose ranges currently used in clinical settings.

In this clinical trial, we will examine whether QMR can quickly and accurately quantify lymphedema severity, as well as evaluating whether we have optimized propranolol usage for treatment of LM patients. The primary endpoints for this study are to: 1) validate QMR as a tool for evaluation of lymphedema, and 2) ascertain whether LM patients can tolerate higher doses of propranolol, as measured by known propranolol adverse effects and patient-reported symptoms. A secondary endpoint will address whether patient-reported LM symptoms and quality of life are improved with higher doses of propranolol; objective findings such as LM size on physical examination and imaging studies will be analyzed as well. In addition, LM tissue biopsies will be acquired from patients before and after propranolol treatment for further analyses of disease progression.

## EXPERIMENTAL DESIGN SCHEMA

The dose escalation for each patient will be as follows (Table 1):

Table 1. Propranolol intra-patient dose escalation schedule and assessments

	Propranolol Dose Schedule*	Assessments		
		Subjective	Objective	Other
Week 1 (initiation)	0.5 mg/kg/day, divided bid	Entrance Interview, Quality of Life Questionnaire	Physical Exam, Imaging	Blood Draw, a Tissue Biopsy a
Week 2	1 mg/kg/day, divided bid a,b	Quality of Life Questionnaire	Physical Exam	
Week 4	2 mg/kg/day, divided bid a,b	Quality of Life Questionnaire	Physical Exam	Blood Draw
Week 6	3 mg/kg/day, divided bid a,b	Quality of Life Questionnaire	Physical Exam	
Week 8	3 mg/kg/day, divided bid a,b	Exit Interview, Quality of Life Questionnaire	Physical Exam, Imaging	Blood Draw, a Tissue Biopsy a

\*Weight will be rounded to the nearest 10-kg increment

aDose escalation in the absence of clinical contraindications.

bIn the presence of clinical contra-indications, the patients will remain on their current level of dosage, or decreased to the previous level, or have their medications held.

A maximum of 8-weeks of therapy may be administered.

## 1.0 GOALS AND OBJECTIVES (SCIENTIFIC AIMS)

### 1.1 Primary Aims

- 1.1.1 To assess whether QMR can accurately and quantitatively assess lymphedema severity. QMR results will be compared to validated, gold standard quantitation of total body, extracellular and intracellular water distribution using deuterium (“heavy water”) and sodium bromide (NaBr) and whole body MRI.
- 1.1.2 To assess tolerability, and define and describe the toxicities of propranolol, administered two times daily in patients with lymphedema both by
- 1.1.2a subjective patient-reported symptoms (energy levels, fatigue, dizziness, respiratory issues/wheezing, activities of daily living) by validated questionnaires (SF-36, LYMPH—ICF, LYMPH—ICF--LL)
- 1.1.2b objective measures (heart rate, blood pressure) by physical exam

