## 2.0 BACKGROUND

	Primary Endpoint (Aim 1)	Secondary Endpoint (Aim 2)
Subjective Assessment	Questionnaires QOL	Questionnaires
	Short Form 36 Lymph-ICF Lymph-ICF-LL	Symptoms (Drainage, pain) Activity levels Clothing size change
Objective Assessment	Clinical and radiological Exam	Clinical and radiological Exam
	Blood pressure Heart rate Blood sugar Whole Body MRI QMR Deuterium and NaBr	Weight, BMI Limb girth discrepancy CTCAE Grading for Lymphedema Imaging: QMR, whole body MRI Blood and Tissues Circulation biomarkers IHC lymphatic vessel phenotype PIK3CA mutational analysis Next Gen sequencing analysis

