## 8.4 Statistical Analysis

Descriptive statistics will be used to summarize patient characteristics, toxicity data, response data and biomarker expression. Toxicity rates at each dose tested will be presented with 95% exact confidence intervals. Responses will be evaluated among patients treated at the highest tolerable dose. Continuous outcomes will be summarized using mean  $\pm$  standard deviation or median (interquartile range) for non-normal data. Comparisons between groups and response changes from baseline will be evaluated using two-sided t-tests or the non-parametric equivalent Wilcoxon Rank-Sum test (for non-normal data). Association between PIK3CA mutational status and patient response will be assessed using chi-square/Fisher exact test. All analyses will be performed using a type I error of 0.05. Biostatistics will be done using Irving Institute for Clinical and Translational Research statistical services at Columbia University Medical Center.

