## 11.2 Study Design/ Endpoints (Table 2)

11.2.1 **Study design:** Each patient will serve as his/her own control, for comparison of study questionnaires (subjective) and with changes in the clinical measurements and imaging measurements of the anatomic area affected by lymphatic malformation compared before and after treatment (objective). In our experience, children exhibiting responses to propranolol displayed these within 2 weeks of beginning propranolol treatment, with estimated reduction in the overall volume of the affected area exceeding 20%.

11.2.2 **Primary endpoints:** The primary endpoint will be the tolerability of escalating dosage of propranolol both by subjective reporting (survey instrument) as well as objective measurements of vital signs. Survey instruments include a general quality of life (QOL) and function survey (SF-36), as well as validated survey instruments for patients with lymphedema (LYMPH—ICF, LYMPH—LCF—LL)[38, 39].

11.2.3 **Secondary endpoints:** The secondary endpoints of the study will be both subjective and objective evaluation of the lymphedema after propranolol treatment, as measured by both survey instrument and objective measurements (clinical exam and radiological studies), as well as biological assays from tissues obtained from biopsies.

11.2.3.1 We will determine whether higher doses of propranolol are well tolerated in this patient population. Secondarily, we will measure determine whether higher doses correlate with improvement in lymphedema symptoms and signs, and healing or improvement of skin lesions, if present (reduced lymphatic leakage, reduced bleeding). Skin lesions will be photographed at clinical visits, and daily lymphatic fluid losses estimated by weight measurements.

Using MRI and body composition analysis, we will determine whether propranolol decreases lymphedema, alters edema water content and location (intracellular vs. interstitial), or alters adiposity of affected extremity.

We will study the biologic activity of oral propranolol against lymphedema, by examining the expression of progenitor cell markers, lymphatic endothelial cell markers, beta-adrenergic receptor expression, macrophage markers and detection of adipocyte content of biopsy specimens (see table below). Results will be compared to ultrasound and magnetic imaging data.

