#### 11.3.2 Imaging Studies

Lymphedema MRI characteristics before and after propranolol therapy will be assessed and related to clinical outcome, as applicable. Specifically, whole body MRI will be used to evaluate body composition and changes in regional adipose tissue depots in the affected limb[21-23].

Furthermore, changes in body composition (water and fat content) in response to propranolol treatment will be evaluated in this study. To evaluate water content, the standard deuterium dilution technique will be used. Fasting patients will have blood draw before drinking stable deuterium isotopes and sodium bromide and after isotope equilibration (about 3-4 hours). Total body water, extra-cellular and intracellular water content can be calculated[22, 40]. Furthermore, a quantitative magnetic resonance (QMR) system will be used to evaluate body (fat and water) content in response to propranolol treatment[21]. Quantification and analysis of results will be performed by [name].

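### QMR validation is primary in the abstract, aim 1.1.1 and Table 2, but section 11.2.2 names only tolerability, and no section says how agreement between QMR and the reference will be judged

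*Combined protocol and SAP*

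**What the plan says.** **QMR as primary.** The abstract states "The primary endpoints for this study are to: 1) validate QMR as a tool for evaluation of lymphedema", with tolerability of higher doses second. Section 1.1 makes it aim 1.1.1: "To assess whether QMR can accurately and quantitatively assess lymphedema severity". That aim names deuterium and NaBr dilution and whole body MRI as comparators, and total, extracellular and intracellular water as the quantities. Table 2 lists "Whole Body MRI QMR Deuterium and NaBr" in its primary column.

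**QMR not primary.** Section 11.2.2 says "The primary endpoint will be the tolerability of escalating dosage of propranolol", measured by survey and vital signs, and does not mention QMR. Section 11.2.3 puts radiological studies among the secondary endpoints. Section 11.3.2, which sits under the analysis of secondary endpoints, says "a quantitative magnetic resonance (QMR) system will be used to evaluate body (fat and water) content in response to propranolol treatment".

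**Analysis.** Section 8.4 states "Comparisons between groups and response changes from baseline will be evaluated using two-sided t-tests", with a rank-sum test for non-normal data. It adds descriptive summaries, exact intervals for toxicity rates, and chi-square or Fisher tests for PIK3CA status.

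**Data.** Table 6 schedules QMR, MRI and the body water evaluation together, pre-study and at week 8. Section 11.1 anticipates 15-20 patients, based on clinical volume.

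**The concern.** There are two linked problems. The documents disagree on whether QMR validation is a primary endpoint. And if it is, nothing says how the aim would be answered or what result would count as success.

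The abstract acknowledges that QMR has not been validated for lymphedema, so the validation result has to stand on this trial. Without a statistic and a criterion chosen beforehand, almost any pattern of differences between QMR and dilution could later be described as validation. A method comparison also cannot be read from a significance test: failing to find a difference in a small sample is not evidence that two methods agree.

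**Working it through.** **Step 1: what is specified for aim 1.1.1.**

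| Element | Where | Given? |
|---|---|---|
| Reference methods | Aim 1.1.1 | Yes |
| Water compartments | Aim 1.1.1 | Yes |
| Visits with paired data | Table 6 | Yes: pre-study and week 8 |
| Primary visit for the comparison | – | No |
| Agreement statistic (bias, limits of agreement, concordance, regression on the reference) | – | No |
| Acceptance limit and rule | – | No |
| Permitted interval between the QMR and dilution measurements | – | No |

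Aim 1.1.1 says that results will be compared, and section 11.3.2 says who will analyse them. Neither gives a method. Section 11.3.2 also says "whole body MRI will be used to evaluate body composition and changes in regional adipose tissue depots", so the water comparison rests on dilution.

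**Step 2: the plan's own figure.** There is no power, SD, margin or precision figure to reproduce. The accrual arithmetic is consistent: 8-10 patients per year × 2 years = 16-20, against the stated 15-20.

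**Step 3: why a t-test would not do (illustration only).** Section 8.4 does not assign a t-test to QMR against dilution. Suppose one were used: paired, two-sided 0.05, noncentral t, with bias in units of the SD of the QMR-minus-dilution differences. Biases of 0.5 and 0.25 SD are assumed.

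| True bias | Power, n=15 | Power, n=20 | Chance of a non-significant result |
|---|---|---|---|
| 0.5 SD | 0.438 | 0.564 | 56% / 44% |
| 0.25 SD (same bias, SD doubled) | 0.147 | 0.186 | 85% / 81% |

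For a fixed bias, more scatter between the methods makes a non-significant result more likely, so a worse instrument would look more acceptable.

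**Step 4: precision of an agreement analysis at the planned size.** One pair per patient, in units of the SD of the differences.

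Mean bias, 95% CI half-width = t(0.975, n−1)/√n:
- n=15: 2.145/√15 = 0.55
- n=20: 2.093/√20 = 0.47

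Each limit of agreement, 95% CI half-width = t(0.975, n−1) × √(1/n + 1.96²/(2(n−1))):
- n=15: 2.145 × √(0.0667 + 0.1372) = 2.145 × 0.4515 = 0.97
- n=20: 2.093 × √(0.0500 + 0.1011) = 2.093 × 0.3887 = 0.81

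**The case against.** The best defence is that section 11.2.2 is only an incomplete restatement. Its heading is plural and section 11.2 refers to Table 2, where QMR stands in the primary column. Much of the comparison is also laid out already: references, compartments and visits. That stands as far as it goes. It makes the hierarchy easy to repair, but it supplies neither the statistic nor the criterion.

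A reader might also infer stronger points that the documents do not support:

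- *That response assessment depends on QMR alone.* The abstract's hypothesis casts QMR as the response evaluator, but aim 1.2.1b and section 12.4 rely on MRI, examination and questionnaires. QMR is one response measure among several.
- *That the paired measurements may be four weeks apart.* Section 8.1 allows scans up to 4 weeks and baseline evaluations up to 2 weeks before therapy, but it does not say that QMR counts as a scan. Section 3.1 includes MRI among the baseline evaluations due before treatment within 14 days. All that can be said is that no pairing interval is stated.
- *That dropout would erode the validation at both visits.* The pre-study pair is collected before treatment, so removal during treatment can affect only the week-8 pair. Section 10.1 still requires follow-up data after protocol therapy ends, unless consent is withdrawn.
- *That low t-test power is itself a flaw in the plan.* The plan does not propose that test for this aim. The flaw is an omission.

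**Conclusion.** The point holds and must be fixed. The statements of the primary endpoint contradict each other, and the plan as written cannot answer its first primary aim because it has no agreement analysis and no criterion. This conclusion rests on the text and needs no numerical assumption.

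The precision figures in Step 4 assume roughly normal differences and one usable pair from every patient. They cannot be turned into litres, because the documents give no SD. They show that each limit of agreement would be uncertain by close to one SD of the differences in either direction, so validation at 15-20 patients may be only preliminary.

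**What to change.** 1. **Reconcile the hierarchy.** Make section 11.2.2 agree with the abstract, aim 1.1.1 and Table 2: either name QMR agreement there as a primary endpoint or demote it everywhere.
2. **If it stays primary, add the analysis to section 8.4.** Compare QMR with dilution within patients, for each water compartment that QMR reports. Give mean bias and limits of agreement with 95% CIs. Make the pre-study pair the main analysis and week 8 supporting, and allow for repeated pairs per patient if visits are pooled.
3. **Before data are seen,** have the sponsor set and justify an acceptance limit and the rule for meeting it, and state the permitted interval between the paired measurements.
4. **State the expected precision** from Step 4, and that the validation may be preliminary.

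Agreement in the change to week 8, and relations of QMR to limb girth, MRI and "CTCAE Grading for Lymphedema" (already in Table 2's secondary column), are optional and should be labelled exploratory.

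The cost is a text change in sections 11.2.2 and 8.4, modest analysis work, and a pairing interval that may constrain scheduling. No new measurements are needed, since Table 6 already schedules them.

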### 4.1 Inclusion Criteria

- 4.1.1 Age: Patients must be  $\geq 12$  years of age at the time of study enrollment.
- 4.1.2a Diagnosis: Patients must have a clinically, pathologically, and/or radiographically diagnosed (lymphscintogram or MRI) lymphedema affecting an extremity without prior surgical intervention or major trauma at that extremity.
- 4.1.3 Disease Status: Patients must have either measurable or evaluable disease (see Sections 12.2 and 12.3 for definitions).
- 4.1.4 Therapeutic Options: Patient's current disease state must be one for which there is no known curative therapy or therapy proven to prolong survival with an acceptable quality of life.
- 4.1.5 Performance Level: Karnofsky  $\geq 50\%$  for patients  $> 16$  years of age and Lansky  $\geq 50$  for patients  $\geq 12$  to  $\leq 16$  years of age. Patients who are unable to walk because of paralysis, but who are up in a wheelchair, will be considered ambulatory for the purpose of assessing the performance score.
- 4.1.6 Prior Therapy  
Prior therapy may have included surgery or interventional radiology procedures,

but must have occurred  $> 4$  weeks prior to baseline imaging studies and study entry. Prior therapy may have included other investigational drugs (e.g. sirolimus, sildenafil), since there are no standard medical therapies for lymphedema, but must have concluded  $> 4$  weeks prior to baseline imaging studies.

4.1.7 **Organ Function Requirements**

These are required for enrolled patients with LMs.

4.1.7.1 Adequate Bone Marrow and Renal Function Defined as:

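### Aim 1.1.1 sets out to validate QMR for lymphedema severity, but the plan never relates QMR to limb swelling or lymphedema grade, so the step from body water to severity is untested

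*Combined protocol and SAP*

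**What the plan says.** The construct is stated in section 1.1.1: "To assess whether QMR can accurately and quantitatively assess lymphedema severity". The comparators follow in the same item: "QMR results will be compared to validated, gold standard quantitation of total body, extracellular and intracellular water distribution", by deuterium "and sodium bromide (NaBr) and whole body MRI". Table 2 lists the same tools under the primary endpoint.

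The link from body water to severity is in the Abstract, which says QMR has the potential to "quantify the severity of extracellular water accumulation, thus severity of lymphedema". The Abstract also says that QMR has not yet been validated for lymphedema.

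Eligibility (section 4.1.2a) requires "lymphedema affecting an extremity", from age 12 into adulthood (sections 4.1.1 and 11.6). Section 11.3.2 describes the instruments: "whole body MRI will be used to evaluate body composition and changes in regional adipose tissue depots in the affected limb", and "a quantitative magnetic resonance (QMR) system will be used to evaluate body (fat and water) content in response to propranolol treatment". It names no limb-specific QMR output.

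Limb girth discrepancy and CTCAE grading of lymphedema appear only as secondary response measures (section 1.2.1b and Table 2). Section 12.3 fixes the girth landmarks on the affected and unaffected limb. Section 11.3.2 relates MRI, but not QMR, to clinical outcome. Section 8.4 gives no agreement statistic, water compartment or acceptance threshold for QMR.

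**The concern.** The property to be validated is severity of a regional disease. The comparators with a stated quantity measure water in the whole body. Agreement with dilution would show that QMR reads body water. It would not show that QMR ranks patients by how swollen the limb is, or follows a change in that swelling.

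Patients run from age 12 to adults with no size limit, so body size may account for much of the spread in whole-body water. If it does, two methods can agree closely because both register body size. The first primary aim could then be reported as met without any evidence on the construct it names.

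**Working it through.** **The plan's own figures.** Section 11.1 expects 15 to 20 patients over 24 months. The accrual rate gives 8 × 2 = 16 to 10 × 2 = 20, which is consistent. This is a feasibility figure. No power, precision or agreement target is attached to aim 1.1.1, so there is nothing further to reproduce.

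**Which comparison covers what.**
- Deuterium and bromide dilution: total, extracellular and intracellular water of the whole body. Compared with QMR.
- Whole body MRI: named as a comparator, quantity not stated. The limb readout in 11.3.2 is fat.
- Limb girth discrepancy and CTCAE lymphedema grade: not compared with QMR in any section.

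**How much agreement could a device blind to limb fluid show?** Let B be body water outside the excess limb fluid and L the excess limb fluid, independent, with SDs s and l. Let each method have independent error with SD e. Dilution = B + L + error. QMR = B + wL + error, where w = 1 means it sees limb fluid and w = 0 means it does not.

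- r(QMR, dilution) = (s² + w·l²) / √[(s² + w²l² + e²)(s² + l² + e²)]
- r(QMR, limb fluid) = w·l / √(s² + w²l² + e²)

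All SDs are assumptions: s of 2 to 4 L for an extracellular-type spread or 6 to 8 L for total body water, l of 0.5 to 2 L, e of 0 to 1 L.

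| s, l, e (L) | Blind: r with dilution | Sensitive: r with dilution | Sensitive: r with limb fluid |
|---|---|---|---|
| 3, 1, 0 | 0.949 | 1 | 0.316 |
| 2, 1.5, 0 | 0.80 | 1 | 0.60 |
| 4, 0.5, 0 | 0.992 | 1 | 0.124 |
| 3, 1, 0.5 | 0.924 | 0.976 | 0.312 |
| 2, 2, 1 | 0.596 | 0.889 | 0.667 |
| 6, 1, 1 | 0.960 | 0.974 | 0.162 |
| 8, 0.5, 0.5 | 0.994 | 0.996 | 0.062 |

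For example, the sixth row, blind: 36/√(37 × 38) = 0.960; sensitive: 37/38 = 0.974. The blind device always has zero correlation with limb fluid. At n = 20 the 95% interval around an observed 0.95 (Fisher z, 1.832 ± 1.96/√17) is 0.88 to 0.98, so these two devices could not be told apart. The fifth row shows the limit: when limb fluid varies as much as the rest of extracellular water, blindness lowers the correlation to about 0.6.

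**Within-patient change.** Writing Δ for the change to Week 8, the covariance of a blind QMR with dilution is var(ΔB). Stable body size cancels, so this is small unless other body water shifts. A sensitive device adds var(ΔL). Comparing changes would therefore partly expose a blind device, provided limb fluid changes. The plan does not specify that comparison.

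**What the added analysis can deliver.** The true correlation detectable with 80% power at two-sided 0.05 is tanh[(1.960 + 0.842)/√(n − 3)]: 0.59 for n = 20 and 0.67 for n = 15. An observed 0.70 would have a 95% interval of 0.37 to 0.87 (n = 20) or 0.29 to 0.89 (n = 15).

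**The case against.** The strongest reply is that whole body MRI is a named comparator and images the limb. Section 2.1 speaks of MRI quantifying edema as well as adiposity, and section 11.2.3.1 would use MRI with body composition analysis to see whether edema water and its location change. A reader might infer that QMR is checked solely against whole-body measures. The documents do not support that: MRI could carry limb information. What stands is that 1.1.1 does not name the MRI quantity, and the edema passages describe treatment effects, not a check on QMR.

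A reader might also infer that an invalid QMR would carry through to the efficacy conclusion. The Abstract does give QMR that role, but section 12.4 evaluates response by questionnaires, examination and MRI, section 1.2.1b lists girth and MRI, and Table 2 has QMR as one measure among several. That inference goes too far.

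The correlations rest on assumed SDs and on a cross-sectional correlation that the plan does not itself choose. An analysis of bias would show a blind device as offset by the mean excess limb fluid. This is fair, but no such analysis is specified, and the gap in the text does not depend on the arithmetic.

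Finally, requiring a significant relation with limb girth could reject a good device. A true correlation of 0.32 has power of about 28% at n = 20 and 21% at n = 15. Girth also reflects fat and fibrosis, which section 2.1 describes as part of the disease. This stands, and it rules out a pass/fail gate.

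**Conclusion.** The concern holds in a limited form. Aim 1.1.1 names severity, the comparators with a defined quantity measure whole-body water, and no section relates QMR to limb swelling or lymphedema grade. The step from body water to severity is asserted in the Abstract and left untested. This conclusion rests on the text alone.

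The size is illustrative. Under the assumed SDs, a device missing all excess limb fluid could correlate about 0.6 to 0.99 with dilution across patients. A reader might take this to mean that QMR is blind to limb fluid. Nothing in the documents shows that; they describe QMR as measuring body water. It is a possibility that the planned comparison would not reliably exclude.

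**What to change.** Add to section 1.1.1, with a matching analysis in section 8.4:

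- At baseline, relate QMR water, adjusted for body size, to the affected-versus-unaffected girth discrepancy, to limb volume from the existing MRI where it can be read, and to CTCAE lymphedema grade. Name the MRI quantity.
- Relate the Week 8 change in QMR water to the change in the limb measure and to the change in dilution water.
- Report estimates with confidence intervals, with no significance gate.
- If only agreement with dilution is shown, conclude that QMR agrees with dilution for whole-body water, and make no claim of validity for lymphedema severity.

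The cost is protocol wording, a limb-volume reading from scans already planned, and one analysis. Table 6 already schedules QMR, MRI, body water and limb measurements at pre-study and Week 8, and height and weight at both. Lymphedema grade is in Table 2 but has no row of its own in Table 6, so its recording at those visits should be stated. The downside is that the QMR claim may become narrower.
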